This statistical analysis plan (SAP) describes the planned statistical methods to be used during the reporting and analysis of data collected under the Clinical Investigation Protocol Luminopia One Amblyopia Vision Improvement Study. This SAP should be read in conjunction with case report forms (CRFs). This version of the SAP has been developed with respect to the Clinical Investigation Protocol Luminopia One Amblyopia Vision Improvement Study Version 2.0 Amendment 1 08Oct2018. Any revisions to the protocol or CRFs that impact the planned analyses may require updates to the SAP. Analyses not specified in this SAP will be considered post-hoc and exploratory in nature. The SAP considers VA values in true logMAR scores; the protocol reports VA in lines, where 1 line is equal to 0.10 logMAR.

2 Abbreviations

Abbreviation/Term	Definition
AE	Adverse Event
AT	As-Treated
BCVA	Best Corrected Visual Acuity
CIP	Clinical Investigation Plan
CRF	Case Report Form
eCRF	Electronic Case Report Form
ICF	Informed Consent Form
ITT	Intent-to-Treat
PP	Per-Protocol
SAE	Serious Adverse Event
SAP	Statistical Analysis Plan
VA	Visual Acuity

Statistical Analysis Plan		Page 7 of 23
Sponsor Luminopia	Study Luminopia One Amblyopia Vision Improvement Study	

3 Study Objectives

The objective of the study is to demonstrate the safety and efficacy of Luminopia One in patients with amblyopia associated with anisometropia and/or with mild strabismus.

3.1 Primary Efficacy Endpoint

The mean change in amblyopic eye BCVA from baseline to 12 weeks of treatment with Luminopia One compared to mean change in amblyopic eye BCVA from baseline to 12 weeks with refractive correction alone.

3.2 Primary Safety Endpoint

The mean change in fellow eye BCVA from baseline to 12 weeks of treatment with Luminopia One compared to mean change in fellow eye BCVA from baseline to 12 weeks with refractive correction alone.

Additionally, the primary safety endpoint will report the frequency and severity of all related Adverse Events (anticipated and unanticipated).

3.3 Secondary Endpoints

3.3.1 VA at 12 Weeks Defined as a Binary Outcome

The proportion of amblyopic-eye BCVA improvement of ≥ 2 lines (-0.20 logMAR) at 12 weeks (Visit 4) from baseline, in each treatment group.

3.3.2 Stereoacuity at 4, 8 and 12 Weeks

Mean change in stereoacuity from baseline to 4, 8 and 12 weeks, respectively, in each treatment group.

3.3.3 VA at 4 and 8 Weeks

The mean change in amblyopic eye BCVA from baseline to 4 and 8 weeks of treatment with Luminopia One compared to mean change in amblyopic eye BCVA from baseline to 4 and 8 weeks with refractive correction alone.

3.3.4 Adherence at 4, 8 and 12 Weeks

The mean adherence with the Luminopia One therapeutic from baseline to 4, 8, and 12 weeks, in the treatment group.

Statistical Analysis Plan		Page 8 of 23
Sponsor Luminopia	Study Luminopia One Amblyopia Vision Improvement Study	

3.4 Safety Reporting

3.4.1 Adverse Events

The participant and parent(s) will be asked about anticipated and unanticipated adverse events at each visit and phone call. The frequency of known and unknown adverse events will be summarized for all participants.

4 Study Design

The proposed study is a multi-center randomized, controlled, masked, clinical trial which compares mean change in amblyopic eye BCVA from baseline with Luminopia One (“therapeutic”), to refractive correction (“control”). One-hundred and forty participants ($n = 140$) aged 4-7 years (inclusive) will be enrolled. Participants will be randomized 1:1 to the “therapeutic group”, to use Luminopia One, or the “control group”, to undergo continued refractive correction, for 12 weeks of treatment.

A group sequential design with a single interim analysis will be used to allow stopping for either early success or futility in both primary safety and efficacy endpoints. The interim analysis will be conducted after 75% of participants have completed their 12-week follow-up visit. The overall Type I error rate was set at 0.05.

4.1 Randomization

Participants will be randomized at the screening and enrollment visit. Randomization will be performed using a random permuted block design stratified by investigational site with a 1:1 allocation ratio (therapeutic group : control group). Randomized treatment will be assigned from the electronic database randomization assignment module.

4.2 Masking

Due to the nature of the therapy, participants cannot not be masked to the treatment assignment. Stereoacuity and distance visual acuity testing will be conducted by a Masked Examiner who will not have access to treatment group assignment.

Statistical Analysis Plan		Page 9 of 23
Sponsor Luminopia	Study Luminopia One Amblyopia Vision Improvement Study	

5 Sample Size Determination

Sample size estimates were based on data from previous Pediatric Eye Disease Investigator Group (PEDIG) studies (ATS3¹, ATS5², ATS18³ and ATS20) and data from participants in Luminopia One pilot trials who would meet the eligibility criteria for the current protocol.

Control Group –Refractive Correction

To estimate the mean change in amblyopic eye visual acuity for the primary efficacy endpoint, data were reviewed from participants aged 4 to 6 years who were randomly assigned to continue refractive correction alone in a previous PEDIG study (ATS5, see Table 1). The mean change in VA at 5 weeks was -0.055 logMAR (95% CI: -0.019 to -0.090 logMAR) with standard deviation 0.128 logMAR (95% CI: 0.107 to 0.158 logMAR). A negative change in logMAR score of VA from baseline to 5 weeks indicates an improvement in vision.

Given the more stringent eligibility criteria in the proposed study as compared to the previous study, we anticipate that the magnitude and standard deviation of mean change in visual acuity after 12 weeks with refractive correction in the current study will be smaller than those in Table 1. The anticipated improvement in the control group, for the purpose of sample size estimation, was set at -0.045 logMAR by a group of PEDIG investigators and the Sponsor.

To estimate the mean change in fellow eye visual acuity for the primary safety endpoint, data were reviewed from participants who were randomly assigned to continue refractive correction alone in a previous PEDIG study (ATS5, see Table 2). The mean change in VA at 5 weeks was -0.02 logMAR (95% CI: 0.00 to -0.04 logMAR) with standard deviation 0.10 logMAR (95% CI: 0.08 to 0.12 logMAR). A negative change in logMAR score of VA from baseline to 5 weeks indicates an improvement in vision.

Therapeutic Group – Luminopia One

To estimate the mean change in amblyopic eye visual acuity for the primary efficacy endpoint, data from 3 studies were reviewed: (1) data for participants randomly assigned to a similar treatment of “Dig Rush” on an iPad device (E. Birch Study); (2) data from a previous PEDIG trial (ATS18) for participants randomly assigned to a similar treatment of “Hess falling blocks” on an iPad device; and (3) data from Luminopia One pilot trials (Table 1).

To estimate the mean change in fellow eye visual acuity for the primary safety endpoint, data were reviewed from participants aged 4 to 7 years enrolled in Luminopia One pilot trials. The mean change in VA at 12 weeks was -0.05 logMAR (95% CI: -0.02 to -0.08 logMAR) with standard deviation 0.10 logMAR

Statistical Analysis Plan		Page 10 of 23
Sponsor Luminopia	Study Luminopia One Amblyopia Vision Improvement Study	

(95% CI: 0.08 to 0.13 logMAR). A negative change in logMAR score of VA from baseline to 12 weeks indicates an improvement in vision.

Table 1: Previous Study Data (Primary Efficacy Endpoint Reference)

Cohort	N	Change in Amblyopic Eye VA at the 4 -5 Week Visit (dependent on study design)		N	Change in Amblyopic Eye VA at 8-12 Week Visit (dependent on study design) [‡]	
		Mean logMAR) Change (95% CI)	SD Change (95% CI)		Mean logMAR)Change (95% CI)	SD Change (95% CI)
Refractive Correction Alone:						
ATS5: Age 3 to 6 years ¹	53	-0.055 (-0.020 to -0.089)	0.128 (0.107 to 0.158)		n/a	n/a
Binocular Therapeutic:						
E. Birch Study (Age 4 to 6 years) ²	9	-0.167 (-0.089 to -0.245)	0.119 (0.080 to 0.228)		n/a	n/a
Luminopia Pilot Trials (Age 4 to 7 years) ³	34	-0.136 (-0.096 to -0.176)	0.118 (0.095 to 0.155)	35	-0.164 (-0.109 to -0.219)	0.166 (0.134 to 0.217)
ATS18 (Age 5 to 6 years) ⁴	39	-0.115 (-0.073 to -0.157)	0.135 (0.110 to 0.174)	39	-0.123 (-0.079 to -0.167)	0.139 (0.114 to 0.179)
Patching Therapeutic:						
ATS18 (Age 5 to 6 years) ⁴	50	-0.090 (-0.050 to -0.130)	0.145 (0.121 to 0.181)	48	-0.143 (-0.098 to -0.188)	0.162 (0.135 to 0.202)

¹ ATS5 data were limited to randomized participants with an amblyopic-eye VA of 20/40 to 20/200 inclusive with ≥ 3 lines of interocular difference and a fellow-eye VA of 20/25 or better who had stabilized with refractive correction prior to randomization. The baseline magnitude of tropia at near (as measured by SPCT) was limited to <5pd. The outcome data reported were based on the 5-week primary masked outcome visit.

² E. Birch study enrolled children aged 4 to <7 years of age. Change in VA after 4 weeks of binocular therapy was computed for participants randomly assigned to receive binocular the Dig Rush game on an iPad device for 4 weeks (prescribed 1 hour per day, 5 days per week without patching). Participants with >4pd magnitude of strabismus (measured by PACT) were excluded from the study

³ Data from Luminopia pilot trials are limited to participants 4 to 7 years old with ocular alignment ≤ 5 pd.

⁴ ATS18 study participants were prescribed binocular therapy for 1 hour per day, 7 days per week vs 2-hours per day of patching. The binocular game, Hess falling blocks, was played on an iPad device. The outcome data reported are from the 4-week and 8-week masked outcome visits.

Statistical Analysis Plan			Page 11 of 23	
Sponsor Luminopia	Study Luminopia One Amblyopia Vision Improvement Study			

Table 2: Previous Study Data (Primary Safety Endpoint Reference)

Cohort	N	Change in Fellow Eye VA at the 4-5 Week Visit (logMAR)		N	Change in Fellow Eye VA at 12 Week Visit (logMAR) [‡]	
		Mean Change (95% CI)	SD Change (95% CI)		Mean Change (95% CI)	SD Change (95% CI)
Refractive Correction Alone:						
ATS5: Age 3 to 6 years ¹	68	-0.02 (-0.00 to -0.04)	0.10 (0.08 to 0.12)		n/a	n/a
Binocular :						
Luminopia Pilot Trials (Age 4 to 7 years) ³	36	0.00 (-0.02 to 0.02)	0.05 (0.04 to 0.06)	35	-0.05 (-0.02 to -0.08)	0.10 (0.08 to 0.13)

Effect Size Estimates

Efficacy:

Based on Luminopia One pilot trials (Table 1), the estimate for mean change in amblyopic eye visual acuity for the primary efficacy endpoint is -0.164 logMAR in the therapeutic group and -0.045 logMAR in the control group, with a pooled standard deviation of 0.140 logMAR. The pooled standard deviation was estimated from two studies run by PEDIG in the same patient population ATS 18⁴ and ATS 20⁵.

The true difference between the therapeutic and refractive correction might be as large as -0.119 logMAR; however, a conservative approach was taken to detect a true difference as small as -0.075 logMAR, and therefore a group difference of -0.075 logMAR will be used to estimate sample size. There is sufficient evidence supporting the therapeutic's efficacy to justify a one-sided superiority test.

Safety:

Safety will be measured as change in visual acuity in the fellow eye. This is a noninferiority analysis to demonstrate that change of VA in the fellow eye when using Luminopia One is not worse than that observed in the control group.

Based on previous studies of amblyopia where Fellow Eye VA was the safety endpoint (Table 2), the estimate for mean change in fellow eye visual acuity for the primary safety endpoint is -0.05 logMAR in the therapeutic group and -0.02 logMAR in the control group, with a pooled standard deviation of 0.10 logMAR.

Statistical Analysis Plan		Page 12 of 23
Sponsor Luminopia	Study Luminopia One Amblyopia Vision Improvement Study	

A noninferiority margin of +0.10 logMAR (1 line of VA) was determined to be most appropriate, given that 0.10 logMAR is the minimum clinically detectable difference in clinical practice with a standard eye chart for this age group³⁸. Consequently, +0.10 logMAR would be the smallest unacceptable difference in fellow eye visual acuity change between the therapeutic and control groups, and therefore the most appropriate noninferiority margin.

Additionally, the primary safety endpoint will report the frequency and severity of all related Adverse Events (anticipated and unanticipated).

Group Sequential Design:

The sample size for this trial will be based on a group sequential design with a single interim analysis to allow for stopping due to either early success (rejecting the null hypothesis) or futility. The goal of the group sequential design is to conserve precious time and resources and prevent unnecessary enrollment of participants if there is no observed difference in effect between groups **or** if there is a significant effect in favor of Luminopia One. It is important to allow for early stopping for success since there is a real possibility the therapeutic could perform significantly better than expected.

Boundaries for both alpha and beta will be calculated using a power cumulative error spending function. The mathematical form of this spending function is:

$$E(t, \rho) = \begin{cases} 1 & \text{if } t \geq 1 \\ t^\rho & \text{if } 0 < t < 1 \\ 0 & \text{otherwise} \end{cases}$$

where ρ is the power parameter and t is the information fraction.

For beta spending, rho was set to 1.0 which results in a spending function much like the Pocock method (i.e. equal spending between the interim and final analyses). For alpha spending, rho was set to 2.0 resulting a spending function somewhere between that found for the O'Brien-Fleming method and the Pocock method.

The planned interim analysis will also involve an analysis of the primary safety endpoint, including both the test of noninferiority in mean fellow eye BCVA change between groups, and a report of the frequency and severity of all related Adverse Events (anticipated and unanticipated).

Sample Size Estimation

Statistical Analysis Plan		Page 13 of 23
Sponsor Luminopia	Study Luminopia One Amblyopia Vision Improvement Study	

The sample size was calculated using the SEQDESIGN procedure in SAS version 9.3. The alternative reference was set to 0.075 logMAR (0.75 lines). As part of the design statement, the number of analyses was set to 2 where the first analysis was planned after 75% of the expected participants complete their 12-week primary outcome visit, and the second after all participants complete their 12-week primary outcome visit. The method of alpha spending was set to “errfuncpow(rho=2.0)” and the method of beta spending was set to “errfuncpow(rho=1.0).” The “alt” parameter was set to “upper” to indicate a one-sided test, alpha was set to 0.05, and beta was set to 0.10 in order to achieve 90% power. The “stop” parameter was set to “both” in order to have boundaries for both success and futility.

This specification results in an effective sample size of 132 participants (66 per arm) providing 90% power to detect a 0.075 logMAR difference between the therapeutic and control groups using a one-sided test (primary **efficacy** endpoint).

With an equal beta-spending function, if there truly is no treatment effect favoring Luminopia One, the chance of stopping the study early for futility at the interim analysis is approximately 89%.

The primary **safety** endpoint will test noninferiority in fellow eye visual acuity change from baseline to the 12-week primary endpoint. The sample size required to achieve 90% power, for a non-inferiority window of 1.0 line of VA (-0.10 logMAR) with Type I error rate of 0.05, is fewer than 132 participants. Therefore, the primary efficacy endpoint will be used to drive sample size.

Adjusting the effective sample size for a 5% loss to follow-up results in a target enrollment of **140 participants**.

6 Statistical Analyses

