6.9.2 Group Sequential Design

A group sequential design will be employed to allow for early stopping due to either success (rejecting the null hypothesis) or futility. The goal of the group sequential design is to conserve precious time and resources and prevent unnecessary enrollment of participants if there is no observed difference in effect between groups or if there is a significant effect in favor of Luminopia One. It is important to allow for early stopping for success since there is a real possibility the therapeutic could perform significantly better than expected.

Boundaries for both alpha and beta will be calculated using a power cumulative error spending function. The mathematical form of this spending function is:

$$E(t, \rho) = \begin{cases} 1 & \text{if } t \geq 1 \\ t^\rho & \text{if } 0 < t < 1 \\ 0 & \text{otherwise} \end{cases}$$

where ρ is the power parameter and t is the information fraction.

For beta spending, rho was set to 1.0 which results in a spending function much like the Pocock method (i.e. equal spending between the interim and final analyses). For alpha spending, rho was set to 2.0 resulting a spending function somewhere between that found for the O'Brien-Fleming method and the Pocock method.

The planned interim analysis will be conducted after 75% of participants, of the re-estimate sample size, reach their 12-week visit and will also involve an analysis of the primary safety and efficacy endpoint, and a report of the frequency and severity of all related Adverse Events (anticipated and unanticipated). All endpoint analyses will be conducted simultaneously on the same data snapshot.

Minimizing Bias

The interim analysis will be designed to optimize usage of time and resources while controlling the Type I and II error rates and minimizing operational bias, in accordance with FDA's guidance on Adaptive Designs for Medical Devices.

Type I and II Error Rates

Statistical Analysis Plan		Page 22 of 23
Sponsor Luminopia	Study Luminopia One Amblyopia Vision Improvement Study	

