Analyzing interim data during the study can lead to Type I error inflation and increase the chance of a false positive conclusion. The proposed group sequential design controls for Type I error inflation by using the well-established statistical method of alpha-spending, so the Type I error for the overall study is controlled at an acceptable level. A similar approach of a beta-spending function is used to keep the Type II error for the overall study at an acceptable level.

Operational Bias

The details of the group sequential design will be approved prior to collection of study data. To avoid any change in behavior between study personnel and participants before and after the interim analysis, the interim analysis will be conducted by the CRO and Sponsor without the involvement of participating investigators. The Medical Monitor will be informed of the interim analysis findings.

In the event that the study is stopped early for success or futility, randomization will be halted and the Medical Monitor will be asked to make a recommendation as to whether follow-up exams for existing participants should continue.

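### The 132 participants assume a binding futility boundary, but the visible SAP never obliges a stop when it is crossed; one-sided Type I error is 5.0% if it is always obeyed and at most about 5.8% if it is not

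*SAP*

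**What the plan says.** - **Section 4, Study Design:** the sequential design "will be used to allow stopping for either early success or futility", for both primary endpoints. "The overall Type I error rate was set at 0.05".
- **Section 5, Effect Size Estimates:** "a group difference of -0.075 logMAR will be used to estimate sample size", "with a pooled standard deviation of 0.140 logMAR".
- **Section 5, Sample Size Estimation:** two analyses, the first at 75% of participants. Alpha spending uses the power family with rho 2.0, beta spending the same family with rho 1.0. The SEQDESIGN setting is upper "to indicate a one-sided test, alpha was set to 0.05, and beta was set to 0.10 in order to achieve 90% power". Boundaries run in both directions ("in order to have boundaries for both success and futility"). The stated results are 132 participants (66 per arm) and about an 89% chance of an early futility stop when there is no effect.
- **Section 6.9.2:** the design "will be employed to allow for early stopping due to either success (rejecting the null hypothesis) or futility". Under Type I and II Error Rates, alpha spending is said to be used "so the Type I error for the overall study is controlled at an acceptable level". Under Operational Bias, the text describes what follows if the study is stopped. It does not say that crossing the futility line requires stopping.
- **Section 6.6.1.1:** the efficacy endpoint is met at p < 0.05, with no condition on the interim result.

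**The concern.** A futility boundary can be built in two ways. If it is binding, null trials that fall below the line are counted as finished. Their chance of a false positive at the final look is removed, and the final critical value is lowered to use up the alpha that this frees. If it is non-binding, no such credit is taken and the final test is stricter. The first gives a smaller sample size, but its Type I error holds only if the trial really does stop whenever the line is crossed.

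The SAP's figures are those of the first kind, while its visible text states no duty to stop. If the trial continued past the line and then met p < 0.05, the result would be declared a success at an overall error rate above the stated 0.05. Continuing is conceivable. The line lies at an observed benefit in the device's favour, the Sponsor takes part in the interim analysis (section 6.9.2, Operational Bias), and section 4 refers to futility in both primary endpoints without saying what happens if only efficacy crosses. This is separate from the question of which p-value applies at the interim: it remains after the interim threshold is set to 0.0281.

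**Working it through.** **Inputs (SAP sections 4 and 5).** One-sided alpha 0.05; beta 0.10; difference 0.075 logMAR; SD 0.140 logMAR; 1:1 allocation; information fraction t = 0.75; alpha rho 2; beta rho 1.

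**Model.** Z1 and Z2 are the statistics at the two looks, signed so that positive values favour therapy. They are jointly normal with means θ√0.75 and θ and correlation √0.75. With n per arm, θ = 0.075 / (0.140 × √(2/n)), so n = 2 × (0.140 × θ / 0.075)². A fixed design needs 120 in total.

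**Error spent at the interim.**
- Alpha: 0.05 × 0.75² = 0.0281, so interim success is z ≥ 1.909.
- Beta: 0.10 × 0.75 = 0.075, so the futility line is θ√0.75 + Φ⁻¹(0.075).

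**Reproducing the SAP's figures.** θ and the final critical value c were solved numerically so that total alpha is 0.05 and total beta is 0.10.

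| | Binding | Non-binding | SAP |
|---|---|---|---|
| θ | 3.066 | 3.154 | |
| Futility line, z | 1.216 | 1.292 | |
| Final c (one-sided p) | 1.639 (0.0506) | 1.749 (0.0402) | |
| n per arm | 65.5 | 69.3 | 66 |
| N | 131.0, so 132 | 138.6, so 140 | 132 |
| Futility stop if no effect | 88.8% | 90.2% | about 89% |

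The sample size identifies the design as binding. The 89% agrees but separates the two less sharply.

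**Where the line lies.** At 75% of 66 per arm (49.5), z = 1.216 is an observed benefit of 1.216 × 0.140 × √(2/49.5) = 0.034 logMAR, one-sided p = 0.11.

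**Type I error of the binding design (interim z 1.909, final z 1.639).**
- Interim success: 0.0281.
- Between the lines at the interim, then final success: 0.0219.
- Sum, futility always obeyed: 0.0500.
- Below the futility line at the interim, then final success if continued: 0.0085.
- Sum, futility always overruled: 0.0585 (a simulation of 4 million trials gave 0.0586).
- Overruled in half of the crossings: 0.0500 + 0.5 × 0.0085 = 0.0543.

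With section 6.6.1.1's plain p < 0.05 at the final look (z = 1.645) and 0.0281 at the interim, the error is 4.97% if obeyed and 5.80% if always overruled.

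**Non-binding alternative at 132.** θ = 0.075 / (0.140 × √(2/66)) = 3.077; success at p ≤ 0.0281, then p ≤ 0.0402. Type I error is at most 5.0%, reached when futility is always overruled.
- Beta rho 1: power 88.7% with the line at 1.292, or 89.3% with the line at about 1.22; about 89% either way.
- Beta rho 2: interim beta is 0.10 × 0.75² = 0.05625, θ = 3.059, N = 130.4, power at 132 is 90.2% to 90.3%, and the futility stop under no effect is about 86%.

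**The case against.** The SAP can fairly be read as stop-if-crossed. Section 5 gives the probability of crossing the futility line as the chance of stopping, and section 6.9.2 claims control of both error rates, which is true if the boundaries are obeyed. The permissive wording covers success and futility together, so it may only describe what a sequential design makes possible. Section 6.9.1 is not in the supplied text and the protocol is not shown; either could contain a duty to stop. The excess is small: a null trial that crosses the line and continues has just under a 1% chance of final success (0.0085 / 0.888). Choosing between binding and non-binding is also the sponsor's decision, and one sentence declaring the boundary binding would cure the defect.

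Most of this stands, and it limits the point. A reader might infer that the trial's Type I error is 5.8%, or that the SAP makes the futility stop optional. The document supports neither. The first figure is a ceiling that requires every crossing to be overruled. On the second, the visible text is silent; nothing states that the Sponsor may continue or intends to. What the objection does not remove is that the 5% claim depends on an obligation the visible SAP nowhere states, while its final success rule takes no account of the interim outcome.

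**Conclusion.** The point holds as a conditional one and should be corrected. The SAP's 132 is the sample size of a binding design. The claimed 0.05 holds if futility is always obeyed and can be exceeded by at most about 0.8 percentage points if it is not. This rests on a normal approximation, an information fraction of exactly 0.75 and an interim success threshold of 0.0281. The reading of the text is limited to what is visible: a binding rule in section 6.9.1 or the protocol would reduce the matter to adding a cross-reference.

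**What to change.** In sections 5, 6.6.1.1 and 6.9.2, make the futility boundary non-binding. State success as one-sided p ≤ 0.0281 at the 75% look and p ≤ 0.0402 at the final look, both to be recomputed at the actual information fraction. Then either:

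- keep beta rho at 1.0 and restate power at 132 as about 89%; or
- set beta rho to 2.0, which needs 130.4, so 132 and 90% stand, and restate the futility-stop chance as about 86%.

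**Cost.** One rerun of the design program, SAP wording, a stricter final threshold (0.0402 against 0.0506), and either about one point of power or a slightly lower chance of a futility stop. Neither option adds children. Keeping beta rho 1 together with 90% power would need about 140 evaluable children (140 / 0.95, about 148 enrolled); that is not proposed.

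If the sponsor prefers the present design, the SAP must state that the futility boundary is binding and that no success claim can follow once it is crossed. The 132, 90%, 89% and 5% then stand, at the price of giving up any discretion to continue towards a success claim.
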